4.6.3. Clinical Laboratory Tests

Hematology and blood chemistry test results at baseline and each visit time point and corresponding changes from baseline will be summarized descriptively and listing will be provided in detail. CTCAE grades for hematology and blood chemistry will be determined according to the laboratory parameter CTCAE criteria(see Appendix 3). CTCAE Version 5.0 will be used for grading. According to CTCAE Version 5.0, CTCAE grading of some items requires clinical diagnosis or joint judgment of clinical diagnosis and values, which cannot be completely divided by programming, such as hyperglycemia, hypokalemia, hypophosphatemia, hyponatremia and hyperuricemia, CTCAE Version 4.03 will be used for grading. Patients' changes from baseline CTCAE grade to worst postdose CTCAE grade will be summarized using cross-classification tables. Grade 3 or 4 hematology and blood chemistry laboratory abnormalities occurring during treatment will also be summarized separately, as appropriate. Urinalysis results will be presented in listings only.

Actual study days for patients may differ from planned study days between the first dose of study drug in each cycle and the scheduled visit date. In this case, visit-based summaries will categorize assessments based on visit within time window as shown in Appendix 4.

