d. Smoking history, family history and relevant medical history of tumor diagnosis and treatment should be collected for medical history; symptoms, signs, laboratory abnormalities within 4 weeks before signing the informed consent form, medication history within 14 days before signing the informed consent form, and weight change within 6 months (> or < 5%). Results of examinations performed at our hospital within 21 days prior to the first dose (Part I) or randomization (Part II) and meeting the requirements of this protocol prior to signing of informed consent (hematology, biochemistry, and urinalysis should be performed within 7 days prior to the first dose of each trial part, pregnancy should be performed within 21 days prior to the first dose of each trial part, and virology and pregnancy tests may be performed outside hospital) can be used for screening assessments without the need for the same tests during the screening period. Patients who fail the initial screening may not be rescreened (only once) until consultation with the Sponsor 's designated medical representative and approval by the Sponsor.

e. Height will be measured only at Screening and weight will be measured pre-dose every cycle except Screening.

f. Biochemistry tests included aspartate aminotransferase (AST), alanine aminotransferase (ALT), γ-glutamyltransferase (γ-GT), lactate dehydrogenase (LDH), cholesterol (TC), triglyceride (TG), total bilirubin (TBIL), direct bilirubin (DBIL), total protein (TP), albumin (ALB), alkaline phosphatase (ALP), creatine kinase (CK), glucose (GLU), uric acid (UA), blood urea nitrogen (BUN)/urea (Urea), creatinine (Cr), sodium (Na), potassium (K), calcium (Ca), phosphorus (P), magnesium (Mg), and chloride (Cl). The first dose was administered within 7 days after the examination during the screening period, and if the dose was not administered after 7 days of the examination and the investigator assessed that re-judgment was required, an additional examination could be performed, starting from Cycle 2, before dosing on Day 1 of each cycle, and on Day 8.

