IIIIa	mg/dL or > upper limit of	- 10.34 mmol/L	12.92 mmol/L	mmol/L	
	normal ~ 7.75 mmol/L				
Hypertriglyceride	150 mg/dL to 300 mg/dL or	> 300 mg/dL to 500 mg/dL	> 500 mg/dL to 1000 mg/dL	Life Threatening	Death
mia	1.71	or $> 3.42 \text{ mmol/L to } 5.7$	or > 5.7 mmol/L to 11.4	C	
	mmol/L to 3.42 mmol/L	mmol/L	mmol/L		
Blood bilirubin	$>$ upper limit of normal ~ 1.5	Greater than 1.5 to 3.0 times	Greater than 3.0 to 10 times the	Greater than 10 times upper	-
increased	times upper limit of normal	the upper limit of normal	upper limit of normal (normal		
	(normal baseline); $> 1 \sim 1.5$	(normal baseline); greater than	baseline); greater than 3.0 to 10	(normal baseline); greater	
	times baseline (abnormal	1.5 to 3.0 times the baseline	times the baseline (abnormal	than 10 times baseline	
	baseline)	(abnormal baseline)	baseline)	(abnormal baseline)	
Creatinine	> upper limit of normal ~ 1.5	> 1.5 - 3.0 x baseline; > 1.5 -	> 3.0 times baseline value; >	> 6.0 x upper limit of normal	-
increased	times upper limit of normal	3.0 x normal	$3.0 \sim$		
	11	Limit	6.0 x upper limit of normal		
					D. d
Creatinine	Creatinine clearance (CrCl)	$\operatorname{CrCl} 59 \sim 30$	$\operatorname{CrCl} 29 \sim 15$	CrCl Small in 15	Death
clearance rate	less than 60 mL/min/1.73 m2	mL/min/1.73 m2	mL/min/1.73 m2	mL/min/1.73 m2; requiring	
(CrCl)				dialysis or renal transplant	

Product: Trilaciclib Protocol Number: B02B00801-TRIL A-301

Protocol Number:	B02B00801-TRILA-301	Jiangsu Simcere Pharm	aceutical Co., Ltd		
Hypercalcaemia	Corrected serum calcium >	Corrected serum calcium >	Corrected serum calcium > 12.5	Corrected serum calcium >	Death
(Corrected for	upper limit of normal ~ 11.5	11.5 - 12.5 mg/dL;	- 13.5 mg/dL; > 3.1 - 3.4	13.5 mg/dL; > 3.4 mmol/L;	
albumin)	mg/dL; > upper limit of	> 2.9 - 3.1 mmol/L; calcium	mmol/L; calcium	ionized calcium	
	normal	concentration $> 1.5 - 1.6$	concentration $> 1.6 - 1.8$	concentration > 1.8 mmol/L;	
	Limit: $\sim 2.9 \text{ mmol/L};$	mmol/L; symptomatic	mmol/L; hospitalization	life-threatening	
	Ionized calcium		required		
	concentration > upper limit of				
	normal $\sim 1.5 \text{ mmol/L}$				
Hypocalcemia	Corrected serum calcium <	Corrected serum calcium < 8.0	Corrected serum calcium < 7.0	Corrected serum calcium <	Death
(Corrected for	lower limit of normal ~ 8.0	- 7.0 mg/dL; < 2.0 - 1.75	- 6.0 mg/dL; < 1.75 - 1.5	6.0 mg/dL; < 1.5 mmol/L;	

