Hyperkalemia	> upper limit of normal ~ 5.5 mmol/L	> 5.5 - 6.0 mmol/L; intervention	> 6.0 - 7.0 mmol/L; hospitalization required	> 7.0 mmol/L; life- threatening	Death
Hypokalemia (CTCAE 4.03)	< lower limit of normal (LLN) to 3.0 mmol/L	-	< 3.0 - 2.5 mmol/L	< 2.5 mmol/L	-

Protocol Number: B02B00801-TRILA-301 Jiangsu Simcere Pharmaceutical Co., Ltd $< 800 - 500/\text{mm}^3$; < 0.8 - 0.5 $< 500 - 200/\text{mm}^3$: $< 200/\text{mm}^{3}$: < lower limit of normal ~ Lymphocyte $800/\text{mm}^3$: count $x 10^{9}/L$ $< 0.2 \times 10^{9}/L$ $< 0.5 - 0.2 \times 10^{9}/L$ < lower limit of normal ~ 0.8 x $10^{9}/L$ < lower limit of normal ~ $< 1500 - 1000/\text{mm}^3$; < 1.5 - $< 1000 - 500/\text{mm}^3$; < 1.0 - 0.5Neutrophil count $< 500/\text{mm}^{3}$; _ $1500/\text{mm}^{3}$: $1.0 \times 10^{9}/L$ x 10⁹/L $< 0.5 \times 10^{9}/L$ < lower limit of normal ~ 1.5 x $10^{9}/L$ < lower limit of normal ~ 2.5 < 2.5 - 2.0 mg/dL or < 0.8 -< 2.0 - 1.0 mg/dL or < 0.6 - 1.0 mg/dL< 1.0 mg/dL or < 0.3 mmol/L -Hypophosphate mia (CTCAE mg/dL or < lower limit of 0.6 mmol/L0.3 mmol/L4.03) normal ~ 0.8 mmol/LHypomagnesemia | < lower limit of normal ~ 1.2 < 1.2 - 0.9 mg/dL; < 0.5 - 0.4 < 0.9 - 0.7 mg/dL; < 0.4 - 0.3< 0.9 - 0.7 mg/dL;Death mg/dL; < lower limit of normal mmol/L mmol/L < 0.4 - 0.3 mmol/L $\sim 0.5 \text{ mmol/L}$ Hypermagnesaem > upper limit of normal ~ 3.0 -> 3.0 - 8.0 mg/dL;> 8.0 mg/dL; > 3.30 mmol/L; Death ia mg/dL; > upper limit of normal > 1.23 to 3.30 Life Threatening ~ 1.23 mmol/L mmol/L < lower limit of normal < 75.000 to 50.000/mm³: < 50.000 to 25.000/mm³: $< 25.000 / \text{mm}^{3}$: Platelet count _ $75,000/\text{mm}^3$; < lower limit of < $75.0 - 50.0 \times 10^9/\text{L}$ $< 25.0 \text{ x } 10^{9}/\text{L}$ $< 50.0 - 25.0 \times 10^{9}/L$ normal ~ 75.0 x 10 $^{9}/L$

Product: Trilaciclib

Product: Trilaciclib Protocol Number: B02B00801-TRILA-301

Protocol Number:	B02B00801-TRILA-301	Jiangsu Simcere Pharmaceutical Co., Ltd					
Hypernatremia	> upper limit of normal ~ 150 mmol/L	> 150 - 155 mmol/L; intervention	> 155 - 160 mmol/L; hospitalization required	> 160 mmol/L; life- threatening	Death		
Hyponatremia (CTCAE 4.03)	< lower limit of normal ~ 130 mmol/L	-	130 to 120 mmol/L with or without symptoms	< 120 mmol/L	-		
Leucocyte	< lower limit of normal ~ 3000/mm ³ ; < lower limit of normal ~ 3.0 x 10 ⁹ /L	< 3000 - 2000/mm ³ ; < 3.0 - 2.0 x 10 ⁹ /L	< 2000 - 1000/mm ³ ; < 2.0 - 1.0 x 10 ⁹ /L	< 1000/mm ³ ; < 1.0 x 10 ⁹ /L	-		

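### The Grade 4 hypomagnesemia cell in SAP Appendix 3 repeats the Grade 3 range, so magnesium below 0.7 mg/dL has no laboratory grade

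*SAP*

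**What the plan says.** SAP Section 4.6.3 (Clinical Laboratory Tests) sets the rule: "CTCAE grades for hematology and blood chemistry will be determined according to the laboratory parameter CTCAE criteria", with a reference to Appendix 3. It says that CTCAE 5.0 is used, with 4.03 for items that cannot be graded by program under 5.0. Hypomagnesemia is not among the examples given for 4.03.

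Two outputs use these grades. One is the shift table, in which "changes from baseline CTCAE grade to worst postdose CTCAE grade will be summarized using cross-classification tables". The other is a separate summary, as appropriate, of Grade 3 or 4 hematology and chemistry abnormalities during treatment.

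Magnesium is measured. The biochemistry footnote of the SAP test flow sheet (Appendix 2) ends its list with "phosphorus (P), magnesium (Mg), and chloride (Cl", and Protocol Section 7.2.1 lists it too.

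In SAP Appendix 3 the Grade 2 cell of the hypomagnesemia row reads "< 1.2 - 0.9 mg/dL; < 0.5 - 0.4" (mmol/L). The Grade 3 cell and the first part of the Grade 4 cell follow as "< 0.9 - 0.7 mg/dL; < 0.4 - 0.3< 0.9 - 0.7 mg/dL", directly before the Grade 5 entry (death). The next line, "mmol/L mmol/L < 0.4 - 0.3 mmol/L", completes the mmol/L units of Grades 2 and 3 and gives the mmol/L range for Grade 4.

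**The concern.** A grading table should give each abnormal value exactly one grade, and its top laboratory grade should take in everything beyond the grade below it. Here Grade 4 has the same bounds as Grade 3, and nothing lies below them. The lowest magnesium values would be left without a grade, while values that belong to one grade would qualify for two.

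At stake is the accuracy of the programmed laboratory grades for magnesium in the shift table and the Grade 3/4 laboratory summary. Laboratory abnormalities form part of the Part II safety and tolerability secondary endpoint (Protocol Section 2.2).

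**Working it through.** **Inputs.** All limits come from the hypomagnesemia row of SAP Appendix 3. The lower limit of normal (LLN) is not given. I assumed 1.6, 1.7 and 1.9 mg/dL in turn, and 0.7 mmol/L. The choice moves only the top of Grade 1.

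**Rule.** A value has grade g if it is at or above the lower bound and below the upper bound of g.

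| Grade | mg/dL as printed | mmol/L as printed |
|---|---|---|
| 1 | 1.2 to < LLN | 0.5 to < LLN |
| 2 | 0.9 to < 1.2 | 0.4 to < 0.5 |
| 3 | 0.7 to < 0.9 | 0.3 to < 0.4 |
| 4 | 0.7 to < 0.9 | 0.3 to < 0.4 |

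**Step 1: apply the row as printed.**

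| Magnesium, mg/dL | Grade(s) | Magnesium, mmol/L | Grade(s) |
|---|---|---|---|
| 0.3, 0.5, 0.6, 0.69 | none | 0.1, 0.2, 0.29 | none |
| 0.7, 0.8, 0.89 | 3 and 4 | 0.3, 0.35, 0.39 | 3 and 4 |
| 0.9, 1.0 | 2 | 0.4, 0.45 | 2 |
| 1.2, 1.5 | 1 | 0.5, 0.6 | 1 |

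The mg/dL result is the same under all three assumed LLNs. The gap and the overlap appear in both units.

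**Step 2: compare with the other low-value rows that have a numeric Grade 4.** In each of them Grade 4 is open-ended and starts where Grade 3 stops.

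| Row | Grade 3 lower limit | Grade 4 |
|---|---|---|
| Hypophosphatemia | 1.0 mg/dL | < 1.0 mg/dL |
| Hypokalemia | 2.5 mmol/L | < 2.5 mmol/L |
| Hypocalcemia (corrected) | 6.0 mg/dL | < 6.0 mg/dL |
| Hypoglycemia | 30 mg/dL | < 30 mg/dL |
| Hyponatremia | 120 mmol/L | < 120 mmol/L |
| Neutrophils | 0.5 x 10^9/L | < 0.5 x 10^9/L |
| Lymphocytes | 0.2 x 10^9/L | < 0.2 x 10^9/L |
| Platelets | 25 x 10^9/L | < 25 x 10^9/L |
| Leucocytes | 1.0 x 10^9/L | < 1.0 x 10^9/L |
| **Hypomagnesemia** | **0.7 mg/dL** | **0.7 to < 0.9 mg/dL** |

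**Step 3: repeat step 1 with Grade 4 set to < 0.7 mg/dL and < 0.3 mmol/L.** Values of 0.3 to 0.69 mg/dL are Grade 4 only, and 0.7 to 0.89 mg/dL are Grade 3 only. Values of 0.1 to 0.29 mmol/L are Grade 4 only, and 0.3 to 0.39 mmol/L are Grade 3 only. Every tested value has exactly one grade.

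**Step 4: follow the printed row into the outputs.**

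- Below 0.7 mg/dL: no grade, so the value is missing from the Grade 3/4 summary and cannot count as a worst grade in the shift table.
- 0.7 to below 0.9 mg/dL: Grades 3 and 4 both apply. If the program keeps the worse one, the shift table shows Grade 4. A combined Grade 3-or-4 count does not change, because the value belongs there under either grade.

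**The case against.** **The table text is damaged.** In the text extracted from the PDF, this part of Appendix 3 has lost its cell borders, and the hypophosphatemia row just above is garbled in its Grade 3 cell. That calls for a look at the PDF page, but it does not explain the repeat. An extraction fault would have had to copy the Grade 3 range in two units on two lines and also delete the true Grade 4 text. In the garbled hypophosphatemia row the Grade 4 limit survived.

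**CTCAE 5.0 is named, so a programmer has the right source.** This is a fair point, and an alert programmer may never code the printed cell. But Section 4.6.3 sends the programmer to Appendix 3, and the plan should not hold a table that cannot be followed.

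**The consequences are limited.** This stands. Clinically significant laboratory abnormalities are adverse events (Protocol Section 8.1), graded under CTCAE 5.0 (SAP Section 4.6.2). Chemistry results are also summarized descriptively and listed in full (SAP Section 4.6.3). A reader might infer that life-threatening hypomagnesemia would vanish from safety reporting. The documents do not support that, since only the programmed laboratory grade is affected.

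**Two further inferences also fail.**

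- The creatinine clearance row may look like a second error of the same kind, because its Grade 1, "less than 60 mL/min/1.73 m2", contains the higher grades. Worst-grade logic resolves essentially all of that overlap: 45 mL/min meets Grades 1 and 2 and is reported as Grade 2. The biochemistry panel lists creatinine, not its clearance, and nothing shows that the row feeds an on-study table.
- A reader might argue that carboplatin makes very low magnesium likely here. The documents I have make no such link, and the point does not need it. It is enough that magnesium is measured.

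**Conclusion.** The point holds for one cell. As printed, every magnesium value below 0.7 mg/dL (0.3 mmol/L) is ungraded, and every value from 0.7 to below 0.9 mg/dL (0.3 to below 0.4 mmol/L) has two grades. It looks like a copying slip, and it is minor. How many patients it would touch cannot be computed from the documents.

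The effect stops at the programmed laboratory safety tables. The primary endpoint (Cycle 1 DSN) and the sample size do not use magnesium. The Grade 3 and 4 toxicity endpoint in SAP Section 4.4.3.3 uses hematology results only.

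Three assumptions carry the conclusion: the PDF page shows what the extracted text shows; the program follows Appendix 3 literally; and, for the shift to Grade 4, it keeps the worse of two matching grades. The corrected limit is inferred from the pattern of the neighbouring rows, since the CTCAE text is not part of the documents.

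**What to change.** In SAP Appendix 3, replace the Grade 4 hypomagnesemia entry with the open-ended range below the Grade 3 lower limit: < 0.7 mg/dL; < 0.3 mmol/L. Check it against the CTCAE version that the SAP names for this item. Then confirm that the grading program uses the corrected limit, for example by running it on 0.6 and 0.8 mg/dL and checking that it returns Grade 4 and Grade 3.

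The cost is one table cell and one program check. No data collection, analysis method or sample size changes.

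### SAP Appendix 3: a sodium of exactly 130 mmol/L meets both Grade 1 and Grade 3, creatinine clearance Grade 1 has no lower bound, and no rule says which grade applies

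*SAP*

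**What the plan says.** SAP 4.6.3 grades haematology and blood chemistry from the criteria in Appendix 3 (SAP 5.3). It uses the grades twice: "changes from baseline CTCAE grade to worst postdose CTCAE grade will be summarized using cross-classification tables", and "Grade 3 or 4 hematology and blood chemistry laboratory abnormalities occurring during treatment will also be summarized separately, as appropriate". Hyponatraemia is one of the items graded by CTCAE 4.03 because version 5.0 cannot be fully programmed for it.

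In Appendix 3 the hyponatraemia row gives Grade 1 as "< lower limit of normal ~ 130 mmol/L", leaves Grade 2 blank, gives Grade 3 as "130 to 120 mmol/L with or without symptoms", and puts Grade 4 below 120 mmol/L. The hypokalaemia row is also labelled 4.03 and also has no Grade 2. It writes Grade 3 as "< 3.0 - 2.5 mmol/L", with a sign that excludes the upper end.

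The CrCl row gives Grade 1 as "less than 60 mL/min/1.73 m2", Grade 2 as 59 down to 30, Grade 3 as 29 down to 15, and Grade 4 as "CrCl Small in 15", which is evidently below 15.

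**The concern.** A programmed grading table should give each value exactly one grade. Here sodium 130 lies in two cells that are two grades apart, so the choice decides whether that patient appears in the Grade 3/4 chemistry summary. Two programmers following the SAP could produce different tables. Sodium is in the scheduled biochemistry panel, so the case can arise.

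The CrCl Grade 1 cell contains Grades 2 to 4, and a reduced value of 60 or above gets no grade. Other falling parameters, such as sodium, phosphate and platelets, start Grade 1 at the lower limit of normal (LLN) and end it at a stated figure. The CrCl row is also expressed per 1.73 m2, whereas the only CrCl in the protocol (section 4.1, eligibility) is Cockcroft-Gault in mL/min. No conversion is given.

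**Working it through.** The plan states no figure to reproduce. The check applies the printed bounds literally and counts how many grades each value receives.

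**Reading of end points.** End points are taken as included unless a sign excludes them. The potassium row requires this reading: its Grade 1 ends at 3.0 and its Grade 3 starts below 3.0, so 3.0 would have no grade unless Grade 1 includes it.

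**Sodium** (x in mmol/L). The documents give no LLN, so 135, 136 and 137 were each assumed.
- Grade 1: 130 ≤ x < LLN. Grade 3: 120 ≤ x ≤ 130. Grade 4: x < 120.
- Grade 1 and Grade 3 overlap at x = 130 only. In steps of 0.1, 130.0 is the single value with two grades under each assumed LLN.
- With Grade 3 written as 120 ≤ x < 130, no value has two grades and 130 is Grade 1.

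**Creatinine clearance.** Grade 1: x < 60. Grade 2: 30 ≤ x ≤ 59. Grade 3: 15 ≤ x ≤ 29. Grade 4: x < 15.

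| Grades met | Integers 0–59 | Steps of 0.1, 0.0–59.9 |
|---|---|---|
| 1 and 2 | 30 | 291 |
| 1 and 3 | 15 | 141 |
| 1 and 4 | 15 | 150 |
| 1 only | 0 | 18 |
| Total | 60 | 600 |

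The 18 values that meet Grade 1 only are 29.1–29.9 and 59.1–59.9. A clearance of 29.5 is thus Grade 1 alone, although 30 also meets Grade 2 and 29 also meets Grade 3.

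**Is there a tie rule?** The worst-grade wording in SAP 4.6.3 selects the worst of a patient's post-dose results. The worst-case rule in SAP Appendix 4 covers several visits on one day. Neither says which grade a single result takes when it fits two cells.

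**Would taking the higher grade repair it?** For integer CrCl it gives one grade each: 30 values Grade 2, 15 Grade 3, 15 Grade 4. Grade 1 is then left holding only the gaps 29–30 and 59–60, so the cell still needs correcting. For sodium it would send 130 to Grade 3, which the potassium row's convention would not do.

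**Other rows.** ALT with a normal baseline has unsigned lower bounds for Grades 2 and 3, so exactly 3 times and exactly 5 times the upper limit of normal (ULN) each meet two grades. The AST row carries the signs. Hypomagnesaemia appears to print the same range, 0.9 to 0.7 mg/dL, for Grades 3 and 4, but the table text there is partly broken.

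**The case against.** The strongest objection is that the missing sign may have been lost when the PDF was read. In SAP 4.6.7, Table 3 shows a heart rate of 120 and an RR interval of 1200 with no sign, beside lower limits that keep theirs. Parts of Appendix 3 are scrambled as well. This stands as a reason to check the source PDF. It is weakened by the same row: its Grade 1 and Grade 4 cells keep their signs, and the Grade 3 cell is phrased differently from the potassium cell. It does not reach CrCl Grade 1, whose bound is written in words.

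Second, a CrCl grade table may never be produced. The biochemistry panel (Protocol 7.2.1; SAP Appendix 2) lists creatinine, which has its own Appendix 3 row. CrCl appears only as an eligibility criterion, with no scheduled derivation after baseline. This stands, and it is why deleting the row is an acceptable remedy.

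Third, these are descriptive tables, and the separate Grade 3/4 summary is made only as appropriate. The Grade 3/4 toxicity endpoint in SAP 4.4.3.3 is haematological. This also stands and limits the point to table wording.

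**Conclusion.** The point holds as a minor error in the SAP tables. Subject to the PDF check, sodium of exactly 130 mmol/L has two grades and no rule to choose between them. The CrCl Grade 1 cell is wrong as written. Only descriptive chemistry tables are affected; the primary, key secondary and other efficacy endpoints are not.

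A reader might infer more than the documents support:
- **That Grade 3 hyponatraemia is over-counted.** This happens only if results of exactly 130 occur and are coded upward. Coded to Grade 1, nothing is over-counted.
- **That the excess can be given as a percentage.** The documents give no sodium distribution and no reporting precision. Suppose 80 patients whose lowest sodium is normal with mean 133 to 138 and SD 4 to 5. Coding 130 upward then adds about 28% to 81% to the Grade 3 count with integer reporting, where 81% is 1.1 patients on 1.3. With one-decimal reporting it adds about 2.5% to 6.1%. The spread comes from the assumptions and is not an estimate for this trial.
- **That every CrCl below 60 has two grades.** This is true of integers but not of the two gaps.
- **That CrCl grades are unusable.** Taking the highest matching grade gives each integer one grade; the defects are the Grade 1 cell and the two gaps.

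**What to change.** 1. Check the source PDF for the sign in hyponatraemia Grade 3. If it is absent, write the cell as `< 130 - 120 mmol/L`, in line with the potassium and phosphate rows.
2. Give CrCl contiguous bounds: Grade 1 `< LLN - 60`, Grade 2 `< 60 - 30`, Grade 3 `< 30 - 15`, Grade 4 `< 15`. State whether the graded value is in mL/min or per 1.73 m2 and how it is obtained. If CrCl will not be derived after baseline, delete the row.
3. Run the same boundary check on ALT with a normal baseline (at 3 and 5 times ULN) and on hypomagnesaemia Grades 3 and 4.
4. Add one sentence to SAP 4.6.3 or Appendix 3 naming the grade that a single result takes if it meets two cells. This is a backstop and does not replace the corrected bounds.

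The cost is a few table cells, one sentence and the matching grading code. No new data are needed.

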5.4. Appendix 4 Window Visits

During the treatment cycle, if more than one visit occurred within a window visit, the visit closest to the scheduled date was selected; if the distance between two visits and the scheduled date was the same, the visit occurring later was selected as the window visit; and if multiple visits occurred on the same day, the worst case was selected.

	Cycle 1					Cycle 2 and above			Safety Visit	
Visits	D1	D3	D8	D10	D15	End	D1	D8	End	
Scheduled Date	1	3	8	10	15	22	1	8	22	30 (+ 3)
Biochemistry	-3 to 1		2 to 11		12 to 18	19 to end of cycle	-3 to 1	2 to 15	16 to end of cycle	Date of first dose of last cycle to 40 days after first dose
Hematology	-1 to 1	2 to 5	6 to 9	10 to 12	13 to 18	19 to end of cycle	-3 to 1	2 to 15	16 to end of cycle	Date of first dose of last cycle to 40 days after first dose

|--|

^[a] Relative to Day 1 of each cycle

Product: Trilaciclib Protocol Number: B02B00801-TRILA-301

	Cycle 1					Cycle 2 and above			Safety Visit	
Visits	D1	D5	D10	D12	D15	End	D1	D10	End	
Scheduled Date ^[a]	1	5	10	12	15	22	1	10	22	30 (+ 5)
Biochemistry	-3 to 1				2 to 18	19 to end of cycle	-3 to 1	2 to 16	17 to end of cycle	Date of first dose of last cycle to after first dose 42 days
Hematology	-1 to 1	2 to 7	8 to 11	12 to 13	14 to 18	19 to end of cycle	-3 to 1	2 to 16	17 to end of cycle	Date of first dose of last cycle to after first dose 42 days

Visit Window - 2/3L Subject

^[a] Relative to Day 1 of each cycle

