9.1. Test flow table I

	Screenin						t Period ^a cycle, 6 cy					Safety Visit ^b	Survival
	g Period			C	ycle 1			0	Cycle 2 a	nd abov	ve .	~~~~~~~~~~~~~~~~~~~~~~~~~~~~~~~~~~~~~~	Follow-up ^c
	D-21 ~ - 1	D1	D2	D3	D8	D10	D15	D1	D2	D3	D8	+ 30 days	Every 60 days
Window (Days)					± 1	±1	±1	± 3			±1	± 7	± 7
Informed Consent	Х												
Demographic information	Х												
Past medical history ^d	Х												
Checked in/out	Х												
Randomization (Part II only)	X												
ECOG	Х	Х						Х				Х	
Physical examination	Х				Х		Х	Х				Х	
Body height ^e	Х	Х						Х					
Vital signs	Х				Х			Х				Х	
Biochemistry ^f	Х				Х		Х	Х			Х	Х	
Hematology ^g	Х	Х		Х	Х	Х	Х	Х			Х	Х	
Urine test ^h	Х							Х			Х	Х	
12-lead ECG	Х							Х				Х	
Serum Pregnancy ⁱ	Х												
Tumor assessment ^j	Х						ng every 6	± 1 week	k after fi	rst study	drug do	se	
PK (Part I) ^k					Blood san								
PK (Part II) ^k			Part I	I Day 1-	2 Blood s	ampling							
Trilaciclib/Placebo ¹		Х	Х	Х				Х	X	X			
Carboplatin ¹		Х						Х					
Etoposide ¹		Х	Х	Х				Х	Х	Х			
Virology ^m	Х												
AEs	Х	Х	Х	Х	Х	Х	Х	Х	Х	Х	Х	Х	

Table 11 1st line ES-SCLC Patients Study Procedures (EC Protocol)

Version No.: V1.4, March 21, 2022

	Screenin				ך (21 d			Safety Visit ^b	Survival				
	g Period			Cy	ycle 1			0	Cycle 2 a	nd abov	e	Survey visit	Follow-up ^c
	D-21 ~ - 1	D1	D2	D3	D8	D10	D15	D1	D2	D3	D8	+ 30 days	Every 60 days
Window (Days)					±1	± 1	±1	± 3			± 1	± 7	± 7
Concomitant medication	X	Х	Х	Х	Х	Х	Х	Х	Х	Х	Х	Х	
Survival and other anti- tumor conditions													Х

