5.2. Appendix 2 Test Flow Sheet

	Screenin	n (21 days per cycle, 6 cycles)										Safety Visit ^b	Survival
	g Period			Cy	cle 1			C	Cycle 2 a	nd abov	e	~~~y + 1510	Follow-up ^c
	D-21 ~ - 1	D1	D2	D3	D8	D10	D15	D1	D2	D3	D8	+ 30 days	Every 60 days
Window (Days)					±1	±1	±1	± 3			± 1	± 7	± 7
Informed Consent	Х												
Demographic information	Х												
Past medical history ^d	Х												
Checked in/out	Х												
Randomization (Part II only)	Х												
ECOG	Х	Х						Х				Х	
Physical examination	Х				Х		Х	Х				Х	
Body height ^e	Х	Х						Х					
Vital signs	Х				Х			Х				Х	
Biochemistry ^f	Х				Х		Х	Х			Х	Х	
Hematology ^g	Х	Х		Х	Х	Х	Х	Х			Х	Х	
Urine test ^h	Х							Х			Х	Х	
12-lead ECG	Х									Х			
Serum Pregnancy ⁱ	Х												
Tumor assessment ^j	X	Imaging every 6 ± 1 week after first study								drug do	se		
PK (Part I) ^k			Par	t I D1-4 I	Blood san	npling							

Line 1 ES-SCLC Patient Study Flow (EC Protocol)

Protocol Number: B02B0	0801-TRILA-3	01			Jiangsu S	imcere Pha	armaceutica	l Co., Ltd					
	Screenin g Period			C	ן (21 d ycle 1	Freatmen ays per o	it Period cycle, 6 cy	a vcles)	Cycle 2 a	and abov	/e	- Safety Visit ^b	Survival Follow-up °
	D-21 ~ - 1	D1	D2	D3	D8	D10	D15	D1	D2	D3	D8	+ 30 days	Every 60 days
Window (Days)					± 1	± 1	±1	± 3			± 1	± 7	± 7
PK (Part II) ^k			Part I	I Day 1-	2 Blood s	ampling							
Trilaciclib/Placebo ¹		Х	X	Х				X	Х	Х			
Carboplatin ¹		Х						Х					
Etoposide ¹		Х	Х	Х				Х	Х	Х			
Virology ^m	Х												
AEs	Х	Х	Х	Х	Х	Х	Х	Х	Х	Х	Х	X	
Concomitant medication	Х	Х	Х	Х	Х	Х	Х	Х	Х	Х	Х	X	
Survival and other anti- tumor conditions	.11.1	1 • • •	1: 01				••••	1 '1'	1				X

a. Trilaciclib + EC chemotherapy will be administered in 21-day cycles until disease progression, intolerability, or discontinuation of treatment at the investigator 's discretion (eg, 6 cycles of chemotherapy have been completed).

b. Follow-up was performed 30 days (± 7 days) after the last dose, starting a new anticancer therapy (-7 days), or withdrawing from the study (-7 days), whichever came first.

c. Survival follow-up refers to telephone follow-up every 60 days (± 7 days) after the last dose to collect other anti-tumor information until 50% of subjects die.

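### SAP Appendix 4 files a permitted day-early Day 10 (EC) or Day 12 (topotecan) count under the previous visit, and its safety-visit window opens before the last dose

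*SAP*

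**What the plan says.** **Visit schedule.** For EC, Protocol 9.1 lists Cycle 1 days "D1 D2 D3 D8 D10 D15", with ±1 day at D8, D10 and D15. For topotecan, Protocol 9.2 gives ±1 day at D10, D12 and D15. The flow sheets in SAP Appendix 2 carry the same windows, so the SAP's citation of protocol V1.3 rather than V1.4 does not matter here.

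**Analysis windows.** For EC hematology in Cycle 1, SAP Appendix 4 gives D3, D8, D10 and D15 the ranges "2 to 5 6 to 9 10 to 12 13 to 18". For topotecan, D5, D10, D12 and D15 get "2 to 7 8 to 11 12 to 13 14 to 18". The selection rule is: "if more than one visit occurred within a window visit, the visit closest to the scheduled date was selected". For ties, "if the distance between two visits and the scheduled date was the same, the visit occurring later was selected as the window visit". For several counts on one day, the worst is taken.

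**Safety visit.** Footnote b of the SAP Appendix 2 flow sheet says "Follow-up was performed 30 days (± 7 days) after the last dose", or earlier at new anticancer therapy or withdrawal. Appendix 4 sets the EC window as "Date of first dose of last cycle to 40 days after first dose"; the topotecan window has the same start and a limit of 42 days.

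**Where this applies.** SAP 4.6.3 says that "visit-based summaries will categorize assessments based on visit within time window as shown in Appendix 4". SAP 4.4.3.2 summarizes ANC, platelets, ALC and hemoglobin at baseline and each visit, without naming Appendix 4.

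**The concern.** Two parts of Appendix 4 do not agree with the schedule under which the samples are drawn.

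First, the D10 (EC) and D12 (topotecan) ranges start on the scheduled day, while the protocol lets the sample be taken one day before. A site can comply fully and still have the result tabulated under another visit.

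Second, the safety-visit range has no requirement that the sample follow the last dose. It covers the whole dosing period of the last cycle, including the pre-dose Day 1 count.

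At stake are the by-visit tables of the four blood-count parameters, which are listed secondary endpoints, and the safety-visit laboratory tables. D10 and D12 belong to the most closely sampled stretch of Cycle 1 after dosing, so an empty or mislabelled slot there distorts the described time course.

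**Working it through.** **1. Allowed days against assigned days**

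| Visit | Protocol days | Appendix 4 days | Allowed day filed elsewhere |
|---|---|---|---|
| EC D8 | 7–9 | 6–9 | none |
| EC D10 | 9–11 | 10–12 | Day 9, filed as D8 |
| Topotecan D10 | 9–11 | 8–11 | none |
| Topotecan D12 | 11–13 | 12–13 | Day 11, filed as D10 |

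D15 (Days 14–16) is filed correctly in both regimens.

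**2. All allowed pairs.** Each regimen has 3 × 3 = 9 combinations of previous-visit day and later-visit day. Distances are to the previous visit's scheduled day (8 for EC, 10 for topotecan).

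| Previous visit (EC / topotecan) | Later visit (EC / topotecan) | Distances | Result under Appendix 4 |
|---|---|---|---|
| Day 7 / 9 | Day 9 / 11 | 1 and 1 | Tie: the later count becomes D8/D10, and the real D8/D10 count is discarded |
| Day 8 / 10 | Day 9 / 11 | 0 and 1 | The later count is discarded |
| Day 9 / 11 | Day 9 / 11 | same day | The worst value is used |
| any of the three | Day 10–11 / 12–13 | – | Both filed correctly (6 pairs) |

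So 3 of 9 pairs leave D10/D12 empty unless another count falls in its range. The later count itself is discarded in 1 of 9, and the earlier count in 1 of 9.

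**3. Frequency.** The documents give no distribution of visit days. As an assumption, if 10% of D10/D12 counts are drawn a day early, 10% of those slots are emptied (absent another count). If visits fall evenly over the three allowed days, the figure is one third.

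**4. Can the cut-point be moved?** No. The protocol windows share Day 9 (EC) and Day 11 (topotecan). If EC D10 started on Day 9, a permitted D8 count on Day 9 would be filed as D10. Using the scheduled visit label first gives 0 of 9 misfiled pairs in each regimen.

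**5. Safety visit.** Reading the Appendix 4 limits as study days of the last cycle, the upper limits can be reproduced:
- EC: last dosing day 3 + 30 + 7 = Day 40.
- Topotecan: 5 + 30 + 7 = Day 42.

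The routine lower limits would be 3 + 30 − 7 = Day 26 and 5 + 30 − 7 = Day 28. Appendix 4 starts at Day 1 in both.

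*Target day.* Appendix 4 gives 30 (+ 3) for EC and 30 (+ 5) for topotecan without explanation. Read as last dosing day plus 30, the targets are Days 33 and 35. A routine safety count is then at most 7 days away, while a Day 22 count is 33 − 22 = 11 or 35 − 22 = 13 days away, so the real count is chosen. With no real safety count, the latest count in the window is the closest. From Cycle 2 on that is the D8 (EC) or D10 (topotecan) count unless an unscheduled one exists, or the pre-dose Day 1 count if it is the only one.

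Read as Day 30, a real EC visit on Day 40 (distance 10) or topotecan visit on Day 42 (distance 12) loses to a Day 22 count (distance 8), if there is one.

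**6. Overlap with End.** SAP 4.1 ends a last cycle 36 days after its first day, that is Day 37. From Cycle 2 on, the End range starts on Day 16 (EC) or 17 (topotecan) and runs to the end of the cycle. A routine safety count on Days 26–37 (EC) or 28–37 (topotecan) therefore fits both visits, and no rule prevents double use.

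**The case against.** The strongest reply is that the first problem starts in the protocol. Its ±1 windows overlap, so no set of exclusive day ranges can honor both visits, and Day 9 is equally far from Days 8 and 10. That is correct. It explains the mismatch but also shows that day ranges alone cannot resolve it.

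A reader might infer that on-time D10 and D12 counts are generally misfiled and dropped. The documents do not support that. Counts on the scheduled day or a day late are filed correctly, and the later count is itself discarded in only 1 of 9 pairs. If the previous visit was missed, the early count fills that slot and no value is discarded.

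A reader might also call the safety window 25 (26 − 1) or 27 (28 − 1) days too wide. That goes too far, because the flow sheet permits an earlier safety visit at new therapy or withdrawal. What is missing is the condition that the sample follow the last dose. Nor does a stand-in value arise routinely. It needs a missing safety count, or the Day 30 reading of the target, and it assumes that one sample may serve two visits. Appendix 4 neither allows nor forbids this, and its selection rule is introduced for visits during the treatment cycle.

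Finally, the affected outputs are descriptive, full listings are provided, and the time plots are specified by cycle. The link to Appendix 4 is made in SAP 4.6.3, which covers hematology, and not in 4.4.3.2. This limits the weight of the point without removing it.

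**Conclusion.** The point stands with limited reach. Under the stated rules, a compliant EC D10 count on Day 9 or topotecan D12 count on Day 11 is assigned to the previous visit, in 3 of 9 allowed day pairs per regimen. When both visits have counts, one value is lost or the two are merged to the worst. The true frequency cannot be known from the documents. The safety-visit window can admit an on-treatment or pre-dose count when no follow-up count exists, and a real safety count up to Day 37 can also qualify for End.

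The effect is confined to by-visit laboratory summaries, assuming that the 4.4.3.2 tables use the same windows as 4.6.3. A reader might fear for the primary endpoint, but SAP 4.4.1 derives DSN from all counts on actual dates, and 4.4.2.1 does the same for SN. Troughs and Grade 3/4 hematologic toxicity are defined per cycle. The sample size is untouched. The correction should be made because the rule as written gives wrong by-visit values and the remedy is cheap.

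**What to change.** In SAP Appendix 4:

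- Keep the CRF nominal visit whenever the sample lies within that visit's protocol window. Day 9 may then be D8 or D10 for EC, and Day 11 may be D10 or D12 for topotecan. Use the day ranges only for unscheduled or out-of-window samples.
- Define the safety-visit window as 30 ± 7 days after the actual last dose, plus any earlier post-last-dose sample that the CRF labels as the safety visit because of new therapy or withdrawal. Fixed ranges of Days 26–40 and 28–42 would not do, since they assume a complete last cycle. If dosing stops after Day 1, the window is 1 + 30 ± 7 = Days 24–38, and compliant visits on Days 24–25 (EC) or 24–27 (topotecan) would be excluded.
- Replace 30 (+ 3) and 30 (+ 5) with an explicit target of 30 days after the last dose.
- Do not let a sample used for the safety visit also fill End.
- Say in SAP 4.4.3.2 that the same rules apply.

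The cost is SAP wording and a small programming change. No new data are needed, since Protocol 11.2.1 already has the visit name and actual date recorded in the CRF.
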